7.1.2. Incidence of Adverse Events

An overview of TEAEs will be presented overall and by treatment, including the number and percentage of subjects with any:

- TEAEs
- Related TEAEs
- Grade 3 or higher TEAEs
- Maximum severity TEAE (Mild, Moderate, Severe, Life-Threatening, Death)
- TEAEs leading to study treatment discontinuation
- TEAE's leading to study discontinuation
- TEAEs leading to death
- Treatment emergent SAEs
- Related treatment emergent SAEs

All TEAEs will also be presented in a summary table by SOC and PT through end of study participation. A subject may have more than 1 TEAE for an SOC or PT. A subject with 2 or more TEAEs within the same level of summarization will be counted only once in that level. The summary of TEAEs will be presented in descending order from the SOC with the highest total incidence to the SOC to the lowest total incidence. If the total incidence for any 2 or more SOCs are equal, the SOCs will be presented in alphabetical order. The PTs within each SOC will be presented in alphabetical order.

7.1.3. Relationship of Adverse Events to Study Treatment

A summary of TEAEs by relationship to study treatment will be presented in a table by incidence of occurrence. The investigator will provide an assessment of the relationship of the event to the study treatment. The possible relationships are Not Related, Unlikely, Possibly, and Related. In the TEAE relationship table, if a subject reports multiple occurrences of the same TEAE, only the most closely related occurrence will be presented. Not Related and Unlikely Related are considered to be unrelated to the study treatment while Possibly and Related are considered to be related to the study treatment.

All TEAEs will be presented in a summary table for each treatment group and total by SOC, PT, and relationship to study treatment. If a subject has 2 or more TEAEs in the same SOC (or with the same PT) with a different relationship to study treatment, then the subject will be counted under Related. If the relationship information is missing, the TEAE will be considered related in the summary but will be presented as missing in the data listings.

7.1.4. Severity of Adverse Event

Adverse events will be evaluated and documented using the National Institute of Allergy and Infectious Diseases Division of AIDS (DAIDS) Table for Grading the Severity of Adult and Pediatric Adverse Events Corrected Version 2.1 dated July 2017:

- Grade 1 indicates a mild event
- Grade 2 indicates a moderate event
- Grade 3 indicates a severe event
- Grade 4 indicates a potentially life-threatening event
- Grade 5 indicates death

A summary of TEAEs by severity will be presented in a table. The severity that will be presented represents the most extreme severity captured on the CRF page. In the TEAE severity table, if a subject reported multiple occurrences of the same TEAE, only the most severe will be presented. TEAEs that are missing severity will be presented in tables as severe but all TEAEs will be presented in the data listing with a non-imputed severity.

7.1.5. Serious Adverse Events

All treatment-emergent SAEs will be presented in a summary table by treatment group and total by SOC and PT. Treatment-emergent SAEs will also be presented by relationship to the study treatment, SOC and PT for each treatment group and total. All treatment-emergent SAEs will be presented in a listing. Additionally, serious adverse events will be summarized for the long-term follow-up period using the Safety Long-Term Follow-Up population and will not include any treatment discontinuation summaries.

7.1.6. Adverse Events Leading to Treatment Discontinuation

All TEAEs leading to treatment discontinuation will be presented in a table by SOC and PT and in a data listing.

7.1.7. Adverse Events Leading to Study Discontinuation

All TEAEs leading to study discontinuation will be presented in a table by SOC and PT and a data listing.

7.1.8. Proportion of Subjects with Adverse Events through Week 24

The proportion of subjects with adverse events through Week 24 will be summarized for each treatment group and will be analyzed using the same CMH methods as described in Section 8.

7.1.9. Proportion of Subjects with Serious Adverse Events through Week 24

The proportion of subjects with serious adverse events through Week 24 will be summarized for each treatment group and will be analyzed using the same CMH methods as described in Section 8.

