1.1.2. Secondary Objectives

- To evaluate the effect of EDP 235 on COVID-19 clinical symptoms and outcomes
- To evaluate the effect of EDP 235 on SARS-CoV-2 viral load
- To evaluate the pharmacokinetics of EDP 235

[REDACTED]
[REDACTED]
[REDACTED]
[REDACTED]
[REDACTED]

2. Investigational Plan

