3.1. Incomplete and Missing Data

Imputation rules for missing dates of prior/concomitant medications, including COVID-19 vaccinations and prohibited medications, and procedures are provided in [Appendix 14.5](#).

Imputation rules for missing AE data are provided in [Appendix 14.5](#).

Data that are continuous in nature but are reported in the form $<x$, $>x$, $\leq x$, or $\geq x$ (where x is considered as the limit of quantitation) will be set to limit of quantitation value with the following exceptions:

- Efficacy endpoint data will be imputed as detailed in [Appendix 14.5](#).
- PK concentrations data will be imputed as detailed in [Appendix 14.5](#).

- Other incomplete/missing data will not be imputed, unless specified otherwise.

All analyses will be conducted using SAS Version 9.4 or higher. Unless otherwise stated, a two-sided test will be used at a significance level (alpha) of 0.05 for all analyses. Two-sided 95% confidence intervals (CI) will be provided when appropriate.

Summary Tables and Figures will be presented by treatment group and will be labelled as follows:

- “EDP 235 [REDACTED]”
- “EDP 235 [REDACTED]”
- “Placebo”

All subject data will be presented in individual subject data listings. Dates will be shown in subject listings as they have been recorded. Unless otherwise stated, unscheduled visit results will be included in date/time chronological order, within subject listings only. All listings will be sorted by subject number, date/time and visit. The treatment group (randomized) as well as subject’s sex and age will be stated on each listing. Unless otherwise stated, data listings will be based on all subjects randomized.

When no data are available for a table or listing, an empty page with the title will be produced with suitable text (e.g., “There are no records for this table/listing.”). For analyses where convergence or the analysis cannot be performed, “NC” (not calculable) will be presented in summary tables.

For the reporting of this study both CDISC SDTM (SDTM Implementation Guide version 3.3 or later) and ADaM (ADaM Implementation Guide version 1.3 or later) standards will be applied.

[REDACTED]

[REDACTED]

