6.4. Study Treatments

6.4.1. Extent of Treatment Exposure and Compliance

Duration of study treatment in days will be calculated as: last dose date – first dose date + 1 day, regardless of study treatment interruption (i.e., missed dose). Study treatment exposure (total study treatment administered in mg) will be summarized by treatment group and overall using the safety population.

The study treatment compliance will be calculated as: $100 * (\text{total number of days compliant} / \text{number of days of treatment planned per protocol})$, where a day of compliance is defined as taking one capsule per bottle on consecutive days for Days 1 to 5.

Study treatment compliance will be summarized for all subjects in the SAF population with descriptive statistics by treatment group and overall. Additionally, the number and percentages of subjects who completed treatment per protocol and in each compliance category (<80%, ≥80% to ≤100%) will be also presented by treatment group and overall.

A summary of each subject's exposure and compliance will also be presented in a listing.

7. Safety Analysis

The primary objective of the study is to evaluate the safety and tolerability of EDP 235 compared to placebo as assessed by, but not limited to, adverse events, clinical laboratory results, and vital signs. All safety analyses will be conducted on the safety population. Safety data, including treatment emergent adverse events (TEAEs), serious adverse events (SAEs), vital sign measurements, and laboratory values, will be summarized separately by treatment group.

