7.1. Adverse Events

Adverse events will be summarized by the MedDRA version 25.0 or higher using SOC and PT by treatment group and all summary table percentages will be calculated out of the number of subjects in the Safety population. All events of SARS-CoV-2 reinfection will be considered adverse events. Additionally, adverse events will be summarized for the long-term follow-up period using the Safety Long-Term Follow-Up population and will not include any treatment discontinuation summaries.

All AEs will be presented in a data listing.

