7.1.1. Treatment-Emergent Adverse Events

AEs that occur or worsen on or after the date and time of first dose of study treatment through Day 33 are considered Treatment-Emergent Adverse Events (TEAEs) and will be used for safety analyses.

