^a During the Follow-up period (Day 6 through Day 33), if the participant has symptom recurrence or symptom worsening, an unscheduled visit should be done within 2 days of patient reported symptom recurrence or worsening. At the unscheduled visit, NP swabs will be collected in addition to clinical assessments deemed necessary by the Investigator.

^b Screening assessments should occur within 24 hours of randomization.

- c. D1 assessments are to be done only in randomized participants. Randomization, predose baseline measurements, and dosing must occur on the same calendar date.
- d. These assessments should be done predose as baseline measurements
- e. Participants who discontinue treatment before completing 5 days of dosing should return to the study site within 24 hours of their last dose to complete EOT procedures and proceed to complete all follow up assessments 4, 9 and 28 days (EOFU visit) after their last dose of study drug. Participants who discontinue the study before Day 33 (EOFU) should return to the study site within 24 hours and no more than 48 hours later to complete the EOFU procedures.
- f. Visits may be completed at the study site or by study site personnel via a home visit, if feasible.
- g. These assessments are only required for participants who discontinued the study before Day 5 (ie, do not have an EOT visit before discontinuing the study) or participants who discontinued the study after Day 5 and before Day 14. These participants should have an EOFU visit with additional assessments as indicated
- h. For the Week 12 and Week 24 assessments, paper questionnaires may be used for the Global Impression Questions and EQ-5D-5L and transcribed into the eCRF.
- i. At Week 12 and Week 24, study staff will contact each participant to ask if they have COVID-19 signs and symptoms and record that information into the AE eCRF.

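### The Week 24 any-AE comparison in SAP 7.1.8 mixes reinfections, and probably solicited COVID-19 symptoms, into a safety test; the same contrast without them should be added

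*SAP*

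**What the plan says.** Section 7.1.8 of the SAP defines a long-term safety endpoint: "The proportion of subjects with adverse events through Week 24 will be summarized for each treatment group". It adds that this proportion "will be analyzed using the same CMH methods as described in Section 8", meaning a test stratified by age and symptom duration, with a common risk difference and 95% CI, for each EDP 235 arm against placebo. Section 7.1.9 does the same for serious adverse events. These are the only visible safety sections with a between-arm test. Section 3.1 sets the default: "a two-sided test will be used at a significance level (alpha) of 0.05 for all analyses".

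Two other places determine what can count as an AE in that window:

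- Section 7.1: "All events of SARS-CoV-2 reinfection will be considered adverse events".
- Schedule of Study Procedures (Appendix 14.1), footnote i, for Weeks 12 and 24: "study staff will contact each participant to ask if they have COVID-19 signs and symptoms and record that information into the AE eCRF".

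The TEAE definition in Section 7.1.1 is narrower. It covers "AEs that occur or worsen on or after the date and time of first dose of study treatment through Day 33". COVID-19 symptoms are also an efficacy target, because a secondary objective in Section 1.1.2 is "To evaluate the effect of EDP 235 on COVID-19 clinical symptoms and outcomes".

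**The concern.** Section 7.1.8 uses a single yes/no outcome per subject. Once a subject has any AE record, the outcome cannot show whether the record was a drug reaction, a lingering symptom of the treated infection, or a new infection months after a 5-day course. The last two are outcomes of the disease. The symptoms are also actively asked for at two fixed contacts, whereas AEs in general are collected continuously.

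Two consequences follow. Disease records that are equally common in all arms raise every proportion and shrink a real difference in other AEs. Disease records that differ between arms move the difference: fewer on active treatment offset an AE excess, and more on active treatment inflate or create one. In either case the Week 24 risk difference cannot be read on its own as a statement about drug tolerability.

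**Working it through.** **The passages together.** Section 7.1.8 counts any AE to Week 24. Section 7.1 brings reinfections in explicitly. Footnote i puts the solicited symptom answers on the AE form, and no visible text flags or excludes them. That each positive answer becomes a counted AE is therefore the natural reading, but it is an inference.

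**Inputs.** The visible SAP gives no sample size, AE rate, reinfection rate or long-term symptom rate, so it has no figure to reproduce. Every rate and sample size below is an assumption chosen to show a range.

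**Formula.** Let *a* be the risk of any other AE and *d* the risk of a reinfection or solicited-symptom record, assumed independent within an arm (0 = placebo, 1 = active). Then

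P(any AE) = 1 − (1 − a)(1 − d), and RD = (1 − a0)(1 − d0) − (1 − a1)(1 − d1).

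With d0 = d1 = d this reduces to RD = (1 − d)(a1 − a0), so the true difference is multiplied by (1 − d). Independence matters here. If every disease record fell on a subject who already had another AE, there would be no dilution.

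**Results for a = 20% placebo, 35% active.** The last column is the approximate chance of a significant excess on active at an assumed 100 per arm (two-sided 0.05, unstratified approximation).

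| d placebo / active | P(any AE) placebo / active | RD (points) | Chance |
|---|---|---|---|
| none | 20.0% / 35.0% | +15.0 | 66% |
| 10% / 10% | 28.0% / 41.5% | +13.5 | 52% |
| 10% / 5% | 28.0% / 38.25% | +10.25 | 34% |
| 30% / 30% | 44.0% / 54.5% | +10.5 | 32% |
| 30% / 15% | 44.0% / 44.75% | +0.75 | 3% |

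**Results for a = 10% and 20%.** The RD falls from +10.0 to +7.0 points with d = 30% in both arms, to +5.0 with 10% / 5%, and to −1.0 with 30% / 20%.

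**A third set, a = 15% and 25%, assumed 75 per arm.** Without disease records, z = 0.10 / √[(0.15 × 0.85 + 0.25 × 0.75) / 75] = 1.54. With d of 10% to 25% in both arms, the RD is 9.0 to 7.5 points (z 1.23 to 0.94). With d one third lower on active, it is 6.5 to 1.25 points (z 0.90 to 0.16). The starting z is already below 1.96, so this set shows attenuation but no lost conclusion.

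**When could the difference vanish?** Setting RD = 0 gives d1 = 1 − (1 − a0)(1 − d0)/(1 − a1). For 20% / 35% and d0 = 30%, d1 = 1 − 0.80 × 0.70/0.65 = 13.8%. For d0 = 10% the solution is negative, so no benefit on disease could remove the difference. Full masking needs d0 of at least (a1 − a0)/(1 − a0), which is 0.15/0.80 = 18.75% here and 0.10/0.90 = 11.1% for 10% / 20%, and a drug benefit as well.

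**The opposite direction.** With a = 20% in both arms and d = 10% placebo, 15% active, RD = 0.80 × 0.90 − 0.80 × 0.85 = +4.0 points, with no difference at all in other AEs.

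**Who is contacted.** The Week 12 and 24 contacts reach only subjects who consented to long-term follow-up (Section 3.4.7 and the schedule). If half consented (an assumption), a 30% solicited-symptom rate among them would be 15% of the full safety population, and the dilution factor would be 0.85 instead of 0.70.

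**The case against.** The strongest case on the other side is that 7.1.8 does not carry the safety conclusion. The primary endpoint in Table 1 is safety through Day 33, and TEAEs stop there, so the solicited Week 12 and 24 symptoms cannot enter. Reinfections by Day 33 still can. TEAEs are tabulated by SOC and preferred term, relationship and severity, with serious events shown separately. AEs and SAEs are also summarized for the long-term period in the SAF LTFU population, and all AEs are listed. COVID-19 terms would be visible there. This stands, and it limits the point to one supplementary contrast. It does not remove the point: term-level tables do not yield the any-AE risk difference without those terms, because one subject can appear under several terms.

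Second, counting all AEs whatever their cause is a conventional and cautious summary, and some diary symptoms (headache, nausea, vomiting, diarrhea) are ordinary AE terms. This also stands. It is a reason to keep the planned proportion and place a second version beside it.

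Third, Section 5.1 refers to reinfection status at Weeks 12 and 24 and to a Section 8.3.21 that is not in the visible text, so reinfection may be analyzed separately. That is possible, and no omission should be alleged. A separate analysis would still leave these records inside 7.1.8.

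A reader might infer that efficacy leaks into the trial's safety conclusion as a whole and makes the drug look neutral. The document does not support that. The Day 33 tables lie outside the solicited contacts, no visible text gives the Week 24 test a decision role, and no event rates are stated from which masking could be shown.

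**Conclusion.** The point holds for the Week 24 any-AE contrast only. Reinfections are in it by explicit rule, and solicited COVID-19 symptoms are in it on the natural reading of footnote i. Under independence, equal disease record rates of 10% to 30% shrink a true AE difference by the same 10% to 30%. Unequal rates can offset or inflate it. Complete cancellation needs frequent disease records together with a drug benefit. The actual size and direction cannot be derived from the SAP, because every rate and sample size used here is assumed. The protocol's AE reporting rules, which are not shown, could also change how symptom answers are counted. This is a minor, optional improvement to one supplementary analysis, not a defect in the primary safety evaluation.

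**What to change.** Keep the planned all-AE proportion in 7.1.8 and add the following:

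- The same CMH risk difference and 95% CI for each arm against placebo, excluding (a) COVID-19 sign and symptom records arising from the Week 12 and 24 contacts and (b) SARS-CoV-2 reinfections.
- A flag for (a), fixed before unblinding: by record source if the AE form captures it, otherwise by onset after Day 33 plus a pre-specified list of preferred terms.
- (a) and (b) as separate proportions by arm, with (a) based on the SAF LTFU population, since only those subjects were contacted.
- One sentence naming the denominator of 7.1.8. Section 7 says "All safety analyses will be conducted on the safety population", while Section 7.1 uses SAF LTFU for the long-term period.
- A statement that any conclusion on long-term tolerability will rest on both versions.

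The cost is SAP wording, one derived flag agreed under blinding, and a few table rows. Listings do not change. The drawback is some imprecision, because a headache or nausea reported at a Week 12 contact cannot always be told apart from an ordinary AE. Keeping the all-AE version beside the new one limits the harm from that.

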7.2. Clinical Laboratory Evaluations

Central laboratory values will be used for analysis and results will be graded using the National Institute of Allergy and Infectious Diseases Division of AIDS (DAIDS) Table for Grading the Severity of Adult and Pediatric Adverse Events Corrected Version 2.1 dated July 2017.

Laboratory values and change from baseline will be summarized overall and by treatment group for scheduled visits. Shift tables by scheduled visit and worst post-baseline will also be generated by reference range and grade as follows :

Additionally, results will be summarized according to any value greater than the high limit, 2x upper limit of normal (ULN) or 3x ULN and any value less than the lower limit, 2x lower limit of normal (LLN) or 3x LLN (i.e 1/2 of LLN or 1/3 of LLN).

All laboratory data will be included in the data listings. Test values greater than the high limit, 2x ULN, 3x ULN, less than the lower limit, 2x LLN and 3x LLN.

7.2.1. Pregnancy Tests and Follicle-Stimulating Hormone Test

For female subjects only, all pregnancy and follicle-stimulating hormone test results will be presented in a listing.

7.3. Vital Sign Measurements

Vital sign observed, change from baseline and pulse oximetry measurements will be summarized by treatment by visits.

7.4. Electrocardiogram

All Electrocardiogram (ECG) results will be summarized by treatment group and visit in the Safety population and a listing will be presented of all results with abnormalities flagged.

8. Efficacy Analysis

Unless otherwise specified, efficacy analyses will be performed using ITT-c population and the following methods will be implemented:

For time to event endpoints time and date will be used and 24 hours will be considered as a day. Descriptive statistics using the Kaplan-Meier method will include the median, 25th percentile, and 95% CIs (log-negative-log transformation). Additionally, the cumulative event rate (SE) will be summarized by treatment group and presented graphically over time. For between group comparisons, Cox Proportional Hazards models (tie handling will be addressed first using the exact method then with Efron's method if the exact method does not converge) will include treatment group, randomization stratification factors of age (≤ 50 years or 51 to 64 years) and duration of COVID-19 symptoms (≤ 3 days or >3 days and ≤ 5 days), and the baseline value of the endpoint. The hazard ratios with associated 95% CIs (Wald) and p-values (analysis of maximum likelihood estimates) comparing EDP 235 [REDACTED] versus Placebo, and EDP 235 [REDACTED] versus Placebo will be reported. Model assumptions will be checked via a log-negative-log plot and/or Schoenfeld residuals as appropriate. Subjects who do not achieve the specified endpoint will be censored with time imputed as treatment start time as follows:

COVID-19 diary:

- Subjects who have not been followed through the Day 33 visit (discontinuation from study or incomplete follow-up at the time of analysis) or completed Day 33 diary will be censored at Day 33.

Other time to event endpoints:

- Subjects who discontinued from the study will be censored at Day 33.
- Subjects who have completed the Day 33 visit will be censored at Day 33 Visit Date.

For treatment comparisons of change from baseline endpoints, analysis of covariance (ANCOVA) models will include treatment group, randomization stratification factors of age (≤ 50 years or 51 to 64 years) and duration of COVID-19 symptoms (≤ 3 days or >3 days and ≤ 5 days) and baseline value of the endpoint as the covariate. The least-squares means, SE, and 95% CIs will be presented for individual groups and the difference between groups. The p-value for

the difference between groups will also be presented. In addition, a two-sample t-test will be used to compare change from baseline between treatment without covariate adjustment (unadjusted mean difference). The p-value for the difference between groups will also be presented under the pooled test (equal variances assumption). Line graphs for both the adjusted and unadjusted means with corresponding 95% CIs will also be generated for secondary efficacy endpoints.

Proportional endpoints will be summarized by treatment group. A 2x2x2x2x2 Cochran-Mantel-Haenszel (CMH) test will be used to test the association treatment group (EDP 235 [REDACTED] versus Placebo) and the endpoint analyzed while taking into account randomization stratification factors of age (≤ 50 years or 51 to 64 years) and duration of COVID-19 symptoms (≤ 3 days or >3 days and ≤ 5 days). In addition to the p-value, the risk differences and associated 95% CIs will be reported (using the cmh commonriskdiff (test=mh) option in SAS PROC FREQ). A similar 2x2x2x2x2 Cochran-Mantel-Haenszel (CMH) test will be used for EDP 235 [REDACTED] versus Placebo. There is no planned multiplicity control for the analysis of efficacy endpoints.

In addition to the summaries noted above, all data will be presented in listings. If the two EDP 235 treatment groups exhibit similar efficacy, a comparison may be done between the combined EDP 235 treatment groups and placebo.

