Unscheduled visits measurements will be included in the analysis as follows:

- Derivation of baseline and worst post-baseline measurements.
- Individual subject data listings as appropriate.

Unscheduled visits will not be included in the by-visit summary or analyses.

No additional analysis visit windowing will be done other than what is specified for Baseline and worst post-baseline above.

When there are multiple values within an analysis visit for laboratory assessments,, the worst value (and the latest value if applicable) will be used in the analysis. For graded labs, worst is defined as the highest grade and if there is more than one record of the same grade for a given analysis visit, the latest value will be selected for analysis. For non-graded labs, worst is defined as the smallest value for criteria below a certain threshold or the largest value for criteria above a certain threshold. If a subject has a value below the threshold and above the threshold, the value furthest from the threshold will be chosen.

For all other assessments, if there are multiple values within an analysis visit the latest record will be selected for analysis.

All diary data will be summarized based on the actual day.

Time-to-event variables are defined from the date of first dose.

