8.1.1. Primary Analyses

8.1.1.1. Time to Improvement of Targeted COVID-19 Signs/Symptoms using the COVID-19 Symptom Diary through Day 33

Improvement of targeted COVID-19 signs/symptoms is defined by the following the event occurring on the first of 2 consecutive days or on Day 33 when the following criteria are met:

- All symptoms scored as mild, moderate or severe at baseline are scored as mild or absent
- All symptoms scored as absent at baseline are scored as absent

Time to improvement of targeted COVID-19 signs/symptoms through Day 33 will be summarized graphically using Kaplan-Meier plots and analyzed by the Cox proportional hazard model as described in [Section 8](#).

8.1.1.2. Time to SARS-CoV-2 RNA Viral Load TND Assessed by RT-qPCR through Day 33

Time to SARS-CoV-2 RNA to TND is defined as the time between the date of the first dose to the first date of achieving viral load TND.

Time to SARS-CoV-2 RNA TND will be analyzed as described in [Section 8](#).

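### Day 33 completers who are still positive can be censored before TND events found at the same visit, so the reported clearance rate for time to SARS-CoV-2 RNA TND can run well above the observed proportion

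*SAP*

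**What the plan says.** SAP Section 8 sets the scale: "For time to event endpoints time and date will be used and 24 hours will be considered as a day". For subjects without the event it adds: "Subjects who do not achieve the specified endpoint will be censored with time imputed as treatment start time as follows". The bullets that follow give the censoring day.

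- Swab endpoints, completers: "Subjects who have completed the Day 33 visit will be censored at Day 33 Visit Date".
- Swab endpoints, discontinued subjects: "Subjects who discontinued from the study will be censored at Day 33".
- Diary, whether or not follow-up was complete: "or completed Day 33 diary will be censored at Day 33".

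Other sections count in dates. Section 3 says "Time-to-event variables are defined from the date of first dose", and Section 8.1.1.2 defines time to TND as "the time between the date of the first dose to the first date of achieving viral load TND". For the diary, Section 8.1.1.1 lets a single Day 33 entry qualify: "the event occurring on the first of 2 consecutive days or on Day 33 when the following criteria are met".

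Swabs are scheduled on Days 1, 3, 5, 9, 14 and 33 (Section 8.2.7). The Day 33 visit has a ±1 day window (Section 4.1). Time to RNAemia TND (Section 8.3.5) takes its definition from Section 8.1.1.2 and its analysis from Section 8.

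**The concern.** Two subjects swabbed at the same scheduled visit are timed on different clocks. The one still positive is censored at the first-dose clock time on the visit date. The one who is TND has the event at the recorded swab time, because Section 8 substitutes a clock time only for censored subjects. When the swab is later in the day than the first dose was, the subject known to be positive has already left the risk set. The visit window acts in the same direction: a positive swab on Day 32 is censored before a TND result on Day 33 or 34, although both belong to one visit.

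This censoring is informative, since these subjects were tested and had not cleared. Viral TND is exposed because no swab is scheduled between Day 14 and Day 33, so apart from unscheduled swabs every later clearance is found at the last visit. At stake are the cumulative event rate in the table and figure and, depending on how events are spread over visits, the hazard ratio. The only planned sensitivity analysis repeats the same rule in the per-protocol set, which is restricted to Day 33 completers, so it would not show the problem.

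**Working it through.** The SAP as shown gives no sample size, event rate or hazard ratio for this point, so there is no stated figure to reproduce. The time scale, censoring rule, swab days and window come from the SAP. All event shares below are assumptions.

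**1. Censoring time.** Study day = date − first-dose date + 1, so a Day 33 visit is 33 − 1 = 32 days after the first dose. With the first-dose clock time imputed, censoring falls at exactly 32.0 days. A TND swab taken *h* hours later in the day than the first dose has its event at 32 + *h*/24.

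**2. Clock effect, all visits on Day 33.** Assume 100 subjects in an arm: 35 TND by Day 14, 50 first TND at Day 33, 15 never TND. The observed proportion is 85%. Let half of the 50 Day 33 events come after the dose clock time.
- After Day 14: S = 65/100 = 0.65.
- 25 events before 32.0 days: S = 0.65 × (40/65) = 0.40, with 40 at risk.
- 15 censored at 32.0 days: 25 at risk.
- The remaining 25 events exhaust the risk set: S = 0, a final event rate of 100% against 85%.

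With every visit on Day 33, one late event in the arm is enough to give 100%. If every Day 33 swab precedes the dose clock time, the final rate is the correct 85%.

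**3. Window effect on dates alone.** Same arm, with 15/70/15% of visits on Days 32/33/34 and same-date events placed before censoring.
- Day 32: 0.65 × (1 − 7.5/65) = 0.575; 65 − 9.75 = 55.25 remain.
- Day 33: 0.575 × (1 − 35/55.25) = 0.211; 55.25 − 45.5 = 9.75 remain.
- Day 34: 0.211 × (1 − 7.5/9.75) = 0.049.

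The final event rate is about 95% against 85%. With only 13 subjects first TND at Day 33 (72 earlier, 15 never) and a 20/60/20% spread, S runs 0.28 × (25.4/28) = 0.254, then 0.254 × (14.6/22.4) = 0.166, then 0.166 × (3.0/5.6) = 0.089, so about 91%. Using dates throughout therefore removes only part of the error.

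**4. Hazard ratio, viral TND.** Simulation with assumed inputs: Cox model with Efron ties, 75 per arm, true hazard ratio 1.5, 85% TND.

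| Share first TND at Day 33 | HR, written rule | HR, corrected rule |
|---|---|---|
| about 35% | 1.38-1.39 | 1.47 |
| about 13% | 1.47-1.48 | 1.50-1.51 |

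The final Kaplan-Meier rate under the written rule was 97-100%. In a heavier scenario (70 per arm, half of placebo subjects first TND at Day 33, all visits on Day 33), the hazard ratio was 1.36 against 1.44 with a quarter of swabs after the dose clock time and 1.26 against 1.42 with half. It was 1.44, without bias, with none.

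**5. Censoring at each subject's own swab time.** In that heavier scenario this does not repair the analysis: the final rate is still about 99% and the hazard ratio about 1.3. The root cause is treating a visit-assessed endpoint as continuous time. The imputed clock time is one route to it.

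**6. Diary.** With 70 subjects, 60 events before Day 33, one Day 33-only event after the dose clock time and 9 event-free, S falls from 10/70 to 0 once the 9 are censored at 32.0 days. The curve ends at 100% against 61/70 = 87%. The hazard ratio hardly changes: 1.276 against 1.278, with about 0.8 Day 33-only events per 140 subjects (assumed true hazard ratio 1.3 and 90% improved).

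**The case against.** Several points on the other side stand.

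- **The order is not fixed.** The SAP does not say whether Day 33 swabs come before or after the first-dose clock time. With all swabs earlier and all visits on Day 33 there is no bias.
- **The date-based text is the more specific.** Section 8.1.1.2 defines TND by date. On that reading same-day events and censorings tie and the clock effect disappears. But Section 8 says otherwise, the two are not reconciled, and the window effect remains.
- **The hazard-ratio loss rests on an unknown.** It depends on the share first TND at Day 33, which the document does not give.
- **The true proportion is reported elsewhere.** Table 1 lists the proportion TND over time as a separate endpoint, so a reader could notice the discrepancy.
- **Status of the endpoints.** Section 8.1 calls both primary efficacy endpoints, but Table 1 makes safety primary and lists both as secondary.

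A reader might infer more than the document supports. The quoted clause could be taken to mean censoring at time zero, but the bullets that follow it place censoring at Day 33 or the Day 33 visit. It might also seem that the treatment effect is weakened for both lead endpoints. The diary result does not bear this out, and the diary baseline is predose with later entries at the same time ±2 hours, so many Day 33 entries would precede the dose clock time. Nor can a large loss of power be asserted in general: with about a third first TND at Day 33, simulated power fell from 62% to 46%, but with 13% only from 60% to 58%.

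**Conclusion.** The point holds for time to SARS-CoV-2 RNA TND, and for RNAemia TND by the same rule. It should be fixed before analysis. As written, the cumulative event rate at the end of follow-up can exceed the observed proportion TND by about 12 to 15 percentage points (97-100% against 85%), or about 5 to 10 points on dates alone with the window. These sizes rest on assumed event shares, visit spread and clock times. The direction does not, once some Day 33 swabs are later than the dose clock time or visits spread over the window. Attenuation of the hazard ratio ranges from about 0.08 (1.47 to 1.39) with roughly a third first TND at Day 33 to nearly nil at one in eight or fewer, and is larger if half are. For the diary endpoint only the tail of the Kaplan-Meier curve can be affected. Because the bias in the hazard ratio is toward 1, it would not create a false claim of benefit.

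**What to change.** Use one time scale for events and censoring.

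- **Swab endpoints (RNA TND, RNAemia TND):** assign events and event-free completers to the nominal scheduled visit day, with events ordered before censoring at the same visit. Map the end-of-follow-up visit of early treatment stoppers, which is timed 28 days after their last dose, to the same nominal visit. State how an unscheduled swab counts.
- **Diary:** use whole diary days for both, again with events before censoring.
- **Text:** delete the clock-time imputation clause from Section 8 and make Sections 3, 8 and 8.1.1.2 agree.

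Under nominal visit days the final Kaplan-Meier rate returns to about 85% in the examples above. The cost is a few sentences and a small programming change, with no new data. What is lost is timing detail within a visit, which carries little information when clearance can be seen only at visits.
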